5.3.2.5 Arm A: Missing doses

Missed Doses Day 1 dose

As Day 1 dose of CC-486 will be given in the office, this dose should not be missed. If the patient does not meet the criteria to begin a new cycle, then the patient will be reassessed in a week and Cycle X Day 1 will start when the dose is actually given.

Day X dose missed

If the dose held or missed was to be given on any day other than Day 1, the cycle continues per protocol with one dose not given and that dose is just considered omitted.

5.4 Discontinuation of Treatment: Arm A

In the absence of treatment delays due to adverse events, treatment with CC-486 may continue until one of the following criteria applies:

• Interruption of scheduled therapy for greater than four weeks,

- Intercurrent illness that prevents further administration of treatment,
- Adverse event(s) that, in the judgment of the Investigator, may cause severe or permanent harm or which rule out continuation of the treatment regimen
- For any grade 3 and 4 toxicity that recurs despite dose reduction
- Discontinuation of CC-486 for any reason,
- Treatment with other chemotherapeutic or investigational anti-neoplastic drugs,
- Subject decides to withdraw from the study,
- Suspected pregnancy or positive pregnancy, or
- General or specific changes in the subject's condition render the subject unacceptable for further treatment in the judgment of the investigator, or
- Disease recurrence on imaging, or
- Patient has completed one year of therapy with CC-486.

If the subject has visible disease recurrence on imaging or meets any of the aforementioned criteria for removal from study treatment, then the CC-486 or observation phase of this study will conclude and patient will enter the follow-up phase of the study, following the schedule of assessments as described in Section 5.4.2.9.

Mandatory research bloods and tumor biopsies will be obtained at the time of recurrence for both Arm A and Arm B subjects, per the method determined best per the investigator as outlined on the Study Calendar and in Section.

5.4.1 End of Treatment

When coming off of CC-486 therapy, subjects in Arm A will undergo a physical examination, vital signs, weight, ECOG performance status, assessment of adverse events, labs including CBC with differential, serum chemistry and hepatic panel, CA 19-9, PT/PTT and research blood. If any of these were performed within 7 days, they do not need to be repeated. All remaining pills will be collected.

5.5 Follow-up Phase Both Arms

No disease recurrence:

Less than 10% of patients who have undergone surgery will not develop tumor recurrence after adjuvant therapy.

Therefore, if patients have not recurred after one year of therapy with CC- 486 (Arm A) the drug will be discontinued.

Patients in Arm A will undergo a safety assessment 28 days (\pm 2 days) post the last dose of protocol therapy for resolution of toxicity.

Because Arm B patients do not receive study drug, a safety assessment will not be performed.

All patients (Arm A and B) will be then be contacted (ideally) every 3 months on to obtain the following information about recurrence, survival and anti-cancer treatment (2.2 Study Calendar):

- Any further therapy received (records to be obtained)
- Subjective response on therapy (records to be obtained)
- Any CA 19-9 drawn (records to be obtained)
- Any imaging (images to be obtained)

Disease recurrence

At the time of recurrence, Arm A and Arm B subjects will undergo biopsy of the recurrent lesion per the method determined best per the investigator.

Post recurrence images will be also obtained (pre-recurrence images are optional)

Thereafter, attempts to contact patients every 3 months in order to obtain lesion assessments/post recurrence images, CA19-9 and anticancer treatment and survival information as detailed in section 5.4.2. If study team is unable to make contact with patients, information may be obtained through medical and public records. This information will continue to be collected for patients until patients hit second disease progression.

5.6 Concomitant Therapy

5.6.1 Recommended Concomitant Therapy

Subjects should receive full supportive care, including transfusions of blood and blood products, antibiotics, antiemetics, and growth factor support when appropriate.

- It is recommended that all subjects must be pre-medicated for nausea and vomiting prior to the administration of CC-486. Administration of a 5-HT3 serotonin receptor antagonist is recommended prior to CC-486. Antiemetics should be administered at least 30 minutes prior to administration of CC-486. Additional doses may be administered if required. Other antiemetic medications (prochlorperazine, lorazepam, etc.) may also be taken for delayed nausea as needed. Specific anti-emetic regimens are up to the discretion of the investigator.
- 2. Diarrhea: If diarrhea occurs during dosing, an antidiarrheal agent(s) may be used. It is recommended that patients experiencing diarrhea associated with CC-486 be managed according to the guidelines provided in Appendix C, which are based on a publication in

the Journal of Clinical Oncology⁴³. A dose reduction of CC-486 may be appropriate based on the severity of diarrhea observed and the response to treatment intervention.

3. Contraceptive Therapy: Sexually active men and women of child-bearing potential must agree to use effective contraception.

5.6.2 Prohibited Concomitant Therapy

1. Concomitant use of other anti-cancer therapies, including radiation, or other investigational agents is not permitted while subjects are receiving protocol therapy during the treatment phase of the study.

5.7 Treatment adherence

Research center personnel will review the dosing instructions with subjects. Subjects will be asked to maintain a diary to record CC-486 administration (see Appendix B). Subjects will be asked to bring any unused drug and empty drug containers to the research center at their next visit. Research personnel will count and record the number of used and unused drug at each visit and reconcile with the medication diary.

6 Adverse events

6.1 Definitions Adverse Event (AE) Definition

An adverse event is the development of an undesirable medical condition or the deterioration of a pre-existing medical condition following or during exposure to a pharmaceutical product, whether or not considered causally related to the product. An undesirable medical condition can be symptoms (e.g., nausea, chest pain), signs (e.g., tachycardia, enlarged liver) or the abnormal results of an investigation (e.g., laboratory findings, electrocardiogram). In clinical trials, from the time of signing an informed consent, an AE can include an undesirable medical condition occurring at any time, including run-in or washout periods, even if no trial treatment has been administered. For this trial, Adverse Events and Serious Adverse Events will be collected for Arm A patients only, as they are receiving study drug.

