- ¹ If study assessment assessed within 7 days of Cycle 1, Day 1, they do not need to be repeated.
- ² Correlative blood sampling is optional for patients in Arm B except for at screening and at time of visible disease progression.
- ³ For patients assigned to Arm A, research blood will be collected for tumor methylation analysis and other correlative studies on Day 1 of *every* cycle.
- ⁴ For patients assigned to Arm B, research blood will be collected for tumor methylation analysis and other correlative studies at screening and/or Cycle 1 Day 1 and Day 1 of *every third* cycle beginning with Cycle 4 (Cycle 4, 7, 10).
- ⁵ Patients on Arm B can provide this information to study team member over the phone.
- ⁶ Patients on Arm B who opt not to participate in correlative blood sampling may be assessed by their local oncologist for all clinical, laboratory and imaging parameters.
- ⁷ If study assessment was completed within 7 days of noting visible disease progression, they do not need to be repeated.
- ⁸ For Arm A patients, if research blood was collected within one month, it does not need to be repeated. For Arm B patients, if research blood was collected within 3 months, it does not need to be repeated.
- ⁹ Please refer to Appendix A for definition of ECOG performance status.
- ¹⁰ Radiologic imaging of chest/abdomen/pelvis (CT preferred, abdominal/pelvis MRI will be performed for patients with CT contrast allergy) and any other imaging required per RECIST for the particular subject are required at baseline must be obtained within 4 weeks of initiation of therapy.
- ¹¹ Assessment for presence of visible disease will occur prior to every third cycle, beginning with Cycle 4 (Cycles 4, 7, 10). For each individual patient, the same imaging modality should be used at assessment as was used during screening.
- ¹² Obtain a urine or serum pregnancy test at screening no more than 7 days prior to dosing on Day 1.
- ¹³ Tumor biopsies will be obtained at the time of visible disease recurrence for all subjects. Location of biopsy can be primary tumor or site of metastatic disease, as determined by the treating oncologist. Tumor biopsy may be obtained within 4 weeks of visible disease progression or before first dose of chemotherapy, whichever occurs latest.
- ¹⁴ Completed only if FACIT data not collected at time of visible disease progression

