- ¹⁵ Tumor assessments should ideally be performed within a +/- 2 week window every 3 months (Cycle, 4, 7, and 10). However, Tumor assessment may be completed at the patient's oncologist's discretion outside of the ideal window
- ¹⁶ May be obtained any time throughout the study for both Arm A and Arm B patients.
- ¹⁷ Assessment not required for Arm B patients
- ¹⁸ For Arm B patients CA19-9 may be collected outside of the recommended 3 month window at the patient's local oncologist's discretion.
- ¹⁹ Research samples will be collected at the discretion of the PI based on availability of supplies and safety of patient and staff.
- ²⁰ CC-486 dosing (D1-21) research drug may be shipped to patients to limit contact due to COVID-19 precautions. See Section 5.2.9.1 for more details.
- Review of remaining pills and pill diary may be reviewed during a telemedicine visit when drug is unable to be returned to study staff due to COVID-19 precautions. Copies of the pill diary may be submitted to study staff by phone, email, fax, or mychart.

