5.3.2.2 Arm A for first 12 cycles

Arm A patients will be evaluated on Day 1 of every cycle with a physical examination, ECOG performance status, vital signs, weight, CBC with differential, research blood and serum chemistry and hepatic panel. Arm A patients will also complete an assessment of adverse events and reporting of current medications/procedures on Day 1 of every cycle.

Arm A patients will complete a CA 19-9, quality of life assessment and CT scan on Day 1 of every third cycle beginning at Cycle 4.

Arm A subjects will be evaluated for adverse events on Day 1 of each cycle with the NCI CTCAE v4.0 (http://ctep.info.nih.gov) used as a guide for the grading of severity. For Arm A patients, doses will be reduced for hematologic and other non-hematologic toxicities that can be attributed to the study drug. Dose adjustments are to be made according to the system showing the greatest degree of toxicity. When a dose reduction is required for Day 1 of any cycle, no dose re-escalation will be permitted for the duration of study treatment.

NOTE: Arm B patients will not be evaluated for adverse events as they do not receive the study agent.

Criteria to Initiate Treatment

In Arm A, a new course of treatment may begin on the scheduled Day 1 of a new cycle if:

- Absolute neutrophil count $\geq 1500/\text{mm}^3$
- Platelet count $\geq 100,000/\text{mm}^3$
- Serum creatinine levels < 2 mg/dL
- Serum bilirubin levels $\leq 1.5 \text{ mg/dL}$.
- AST (SGOT) and ALT (SGPT) \leq 2.5 x the institutional upper limit (ULN) of the normal range
- Any other drug-related adverse events that may have occurred must have resolved to < Grade 2 severity except grade 2 anorexia and any correctable metabolic abnormality.
- No evidence of visible disease recurrence on imaging (if indicated per Study Schedule, Section 2, to be done prior to cycles 4, 7, and 10)

If these conditions are not met on Day 1 of a new cycle, the subject will be evaluated weekly and a new cycle of treatment will not be initiated until the toxicity has resolved as described above utilizing the dose modifications as depicted below. If the study drug has to be held for > 28 days, study treatment will be discontinued.

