6.2 Adverse Event Reporting

Protocol Chair

The Protocol Chair is ultimately responsible for the required reporting of all adverse events.

Coordinating Center

The Coordinating Center is the central location for the collection and maintenance of documentation of adverse events and is responsible for submitting adverse event reports to the Protocol Chair promptly. The Coordinating Center will maintain documentation of all adverse event reports for each participating site. Adverse event reports submitted to the Coordinating Center must be signed and dated by the participating site's Principal Investigator. Participating sites must use the SKCCC template for reporting adverse events per SKCCC policy. Information to be provided must include:

- Subject ID number, and initials
- Date of the event
- Description of the event
- Description of site's response to the event
- Assessment of the subject's condition
- Subject's status on the study (on study, off study, etc.)
- Attribution of event to study drug

Participating Sites

Participating sites are responsible for reporting adverse events to their IRB according to its specific requirements and to the Coordinating Center as follows:

Fatal Events whether anticipated or unanticipated, and whether or not related to the study must be reported to the Coordinating Center within **24 hours** of the participating site Principal Investigator's learning of the event.

Serious and Unanticipated Adverse Events as defined above must be reported to the Coordinating Center within 24 hours of the participating site Principal Investigator's learning of the event.

Other Serious Adverse Events which may result in a change to the protocol, informed consent, or risk to subjects as specified in the protocol must be reported within three (3) working days of the participating site Principal Investigator's learning of the event.

Adverse Events which result in no change to protocol, informed consent, or risk to subjects must be reported to the Coordinating Center on a monthly basis.

Adverse event reports are to be emailed to the Coordinating Center at . Follow-up reports are to be emailed to the Coordinating Center as necessary.

The investigator must also report follow-up information about SAEs within the same time frames.

If a non-serious AE becomes serious, this and other relevant follow-up information must also be provided within the same time frames described above.

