8.2 Tumor Biopsies

Tumor biopsies will be attempted on all subjects at the time of visible disease recurrence. We will also consent subjects to obtain paraffin-embedded blocks of their original resected pancreatic tumor. Methylation status will be assessed on these samples to correlate with the data received from the plasma analysis. All new biopsy specimens will be stored as fresh tissue at \leq -70°C for extraction of DNA and RNA.

All biopsy specimens will undergo tumor methylation analysis with MSP for select candidate genes (*TMS1*, *ARH1*, etc) as described above. Evaluation of expression of genes that become demethylated post-treatment will be performed using quantitative real-time PCR, whenever possible. Where sufficient tissue is obtained, samples will also be studied using an Infinium Methylation Assay that surveys genome-wide DNA methylation profiles (such as the Illumina HumanMethylation27 BeadChip or the newer Infinium HumanMethylation450 BeadChip). This technology examines approximately 27,500 CpGs in 14,500 regions, including 12,833 well-annotated genes described in the NCBI CCDS database, 144 methylation hotspots in cancer genes, 982 cancer related targets, and 110 microRNA promoters. Results are analyzed using BeadStudio software that allows for data analysis and integration of methylome data with mRNA or miRNA expression array studies. In regions of cancer hotspots, there are 7 CpGs studied on average per

gene. As little as 500ng of input DNA is required for the BeadChip, which allows for investigation of samples collected by laser capture microdissection. We will investigate if the Illumina Infinium chip can be used to define epigenetic signatures between responders and non-responders to oral epigenetic therapy.

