8.2.1.3 Tumor Biopsies

At the time of recurrence, there must be an attempt to obtain tumor samples by FNA or core biopsy from accessible tumor tissue. A maximum of 8 core biopsies (or fine needle aspirates if cores are considered unsafe) will be obtained from each subject. The aspirates will be used to prepare air dried cytologic smears and frozen samples. The first pass will be used for on-site examination of the material, to determine presence and quality of lesional tissue. The remaining biopsy specimens will be flash frozen in liquid nitrogen and then stored as fresh tissue at \leq -70°C for extraction of DNA and RNA. The biopsy specimens will be stored and evaluated in [name]/ [name]'s laboratory.

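### Serious harm from research biopsies and blood draws in the observation arm has no structured collection or procedure attribution, because AE and SAE collection is limited to Arm A

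*Combined protocol and SAP*

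**What the plan says.** **Scope of collection.** Section 6.1 sets the rule: "For this trial, Adverse Events and Serious Adverse Events will be collected for Arm A patients only, as they are receiving study drug". The note in section 5.3.2.2 repeats it: "Arm B patients will not be evaluated for adverse events as they do not receive the study agent". Footnote 17 to the schedule in section 2.1 says "Assessment not required for Arm B patients", although the row for recording adverse events is marked in the progression column headed for both arms. Section 6.2 again words its SAE collection sentence for Arm A only.

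**Procedures in Arm B.** Section 5.4 says "Mandatory research bloods and tumor biopsies will be obtained at the time of recurrence for both Arm A and Arm B subjects". Section 8.2.1.3 gives the extent: "A maximum of 8 core biopsies (or fine needle aspirates if cores are considered unsafe) will be obtained from each subject". Section 8.2 is softer: "Tumor biopsies will be attempted on all subjects at the time of visible disease recurrence". For blood, footnote 2 to the schedule says "Correlative blood sampling is optional for patients in Arm B except for at screening and at time of visible disease progression".

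**Deaths.** Section 6.2 also says "Fatal Events whether anticipated or unanticipated, and whether or not related to the study must be reported to the Coordinating Center", within 24 hours. That sentence names no arm. Section 6.1.1 lists death as a criterion for an SAE.

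**The concern.** The exemption of Arm B rests on one argument: no study drug, so no need to collect events. The argument fits drug toxicity. It does not fit harm from a needle biopsy done for methylation research, which depends on the procedure and not on the arm. Section 6.1 itself accepts that an adverse event can arise before or without any trial treatment.

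If the rule is followed as written, a bleed or infection after a protocol biopsy in Arm B is not collected as an AE or SAE, while the same event in Arm A is. The trial could then finish without a usable count of serious complications from its own research procedure in half of its patients. In addition, a site with a death in Arm B finds one sentence that asks for a report within 24 hours and others that place Arm B outside collection.

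**Working it through.** No stated design figure is in question here, so there is nothing of the plan's to reproduce. The check has two parts: a comparison of the text, and a rough scale.

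**1. The text, side by side**

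- *Is there a protocol procedure in Arm B?* Yes. Sections 3.5, 5.4, 5.5 and 8.2 and schedule footnote 13 all apply the recurrence biopsy to both arms. Research blood is required in Arm B at screening and at progression. Footnote 8 waives the progression draw if blood was taken within the previous 3 months.
- *Is harm from it collected in Arm B?* Sections 5.3.2.2, 6.1 and 6.2 and footnote 17 confine collection to Arm A. No section makes an exception for study procedures.
- *Would a report record procedure as the cause?* The fields listed in section 6.2 ask for attribution to the drug and have no field for attribution to a procedure. Section 6.3.1 likewise asks for causality with respect to the investigational product.
- *Are Arm B deaths reportable within 24 hours?* The fatal-event sentence in section 6.2 has no arm limit. Section 6.1.1 makes death an SAE, and sections 6.1 and 6.2 collect SAEs in Arm A only. The documents do not say which governs.
- *Are Arm B deaths lost altogether?* No. Sections 2.2, 5.5 and 11.3.1 capture them for PFS and OS. What is missing is safety reporting and attribution.

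**2. How many Arm B biopsies could fall due**

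Inputs from section 11.3.4: control median PFS 6 months, accrual 24 months, minimum follow-up 12 months, 30 patients per arm, 10% loss to follow-up. Exponential PFS and uniform accrual are my assumptions.

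- Hazard: λ = ln 2 / 6 = 0.1155 per month.
- Event probability: 1 − [exp(−12λ) − exp(−36λ)] / (24λ) = 1 − (0.25 − 0.0156) / 2.773 = 0.9155.
- Without loss: 30 × 0.9155 = 27.5.
- With 10% loss: 27 × 0.9155 = 24.7.

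So there would be about 25 to 27 PFS events in Arm B. This is an upper limit on biopsies due, because PFS in section 11.3.1 also counts deaths and because not every recurrence can be biopsied.

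**3. Illustration of what might go uncollected**

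The documents give no complication rate, so I assume a range of 1% to 5% per biopsy. The chance of at least one complication among n biopsies is 1 − (1 − p)^n; for example, 1 − 0.98^27 = 0.42.

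| Biopsies n | p = 1% | p = 2% | p = 5% |
|---|---|---|---|
| 20 | 18% | 33% | 64% |
| 27 | 24% | 42% | 75% |

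The expected number at n = 27 is 0.27, 0.54 and 1.35. The row for n = 20 is a round lower figure that allows for biopsies not done.

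**The case against.** The strongest reply has four parts.

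**The biopsy is less than mandatory.** Section 5.4 uses that word, but sections 8.2 and 8.2.1.3 require only an attempt, from tissue that can be reached. Eight cores is a ceiling, and footnote 19 leaves research samples to the investigator's discretion, with safety as one ground. This stands. It lowers the number of procedures but provides no collection when one is done.

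**Other routes exist.** Section 6.3.2 requires the investigator to notify the IRB of serious events under institutional policy, and section 12.1 extends notification to anything that may add risk; neither names an arm. Section 6.3.1, on SAE reports to the drug supplier, is also worded without an arm. Section 10.3 provides safety review by the sponsor and a safety monitoring committee, and section 10.5 provides monthly safety meetings. This stands too. A reader might infer that Arm B procedure harm is wholly unmonitored, and the documents do not support that. What they lack is a defined feed of such events, with procedure attribution, into the safety data that these bodies review.

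**The fatal-event rule need not conflict.** It sits in a list of how sites report adverse events, after section 6.1 has set whose events are collected, and its wording on relatedness concerns causality and not arm. A reader might call it a flat contradiction. That is too strong, since section 6.1 can be read as limiting it. But the text does not say so, and a site could reasonably read it either way.

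**Arm A-only collection is a deliberate choice.** It is reasoned, repeated, and normal for routine events in an observation arm. The toxicity guideline in section 11.3.5 concerns only patients treated with CC-486. I accept this for routine AEs. The stated reason does not reach harm that the trial's own procedures cause.

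**Conclusion.** The point holds in a narrow form. By following its stated rule, the trial leaves serious procedure-related harm in Arm B without structured collection or attribution, and it leaves open whether the 24-hour fatal-event rule applies to Arm B. At most about 25 to 27 of 30 Arm B patients would become due for a biopsy, given a 6-month exponential median, uniform accrual and up to 10% loss. That figure should not be read as a forecast of biopsies, still less of complications, for which the documents give no rate.

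The gap is in Arm B only, because Arm A procedure harm falls under Arm A collection. No estimand, power figure, error rate or stopping boundary changes. The amendment should be made because it is cheap and concerns patient safety, but the point does not threaten the efficacy analysis.

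**What to change.** - **Section 6.1:** narrow the exemption. For Arm B, collect and report SAEs and deaths attributable to protocol-required procedures, namely the recurrence biopsy and research blood draws. Keep the exemption for routine AEs.
- **Section 6.2:** add attribution to study procedure to the report fields, bring the Arm A-only SAE sentence into line, and state whether the 24-hour fatal-event rule applies to Arm B.
- **Section 5.3.2.2 (note) and schedule footnote 17:** amend both to match. Changing section 6.1 alone would create a new inconsistency.
- **Section 6.3.1:** state the arms covered, so that its unrestricted wording agrees with the revised scope.

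The cost is amendment wording, one added report field, and a short safety query after each Arm B biopsy, with a little data entry for any event found.
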